### **3. Disposition and Exit Status**

#### **3.1 Screening Log Data**

A listing of patients that failed screening will be generated for patients that signed informed consent. The listing will include information on demographic characteristic (sex, race and age) and reason for screen failure.

#### **3.2 Disposition and Exit Status**

Patient disposition (enrolled, completed, discontinued, and reason for discontinuation) will be presented according to the dose (grouped to the nearest dose group, ie, 25, 50, or 100 U of BOTOX) received at the first treatment cycle, as well as an overall BOTOX group (ie, regardless of dose). Data will also be presented by BOTOX treatment cycle.

A listing will be generated for discontinued patients with the corresponding reason(s) for early withdrawal from the study. A data listing for the patients discontinued due to AEs will be presented.

A summary table will be generated for the number of patients who switched from one dose to the next higher dose (remaining on the same dose or a dose escalation).

#### **3.3 Study Duration**

Patients will participate in the study for at least 96 weeks following entry into the study and should have at least 12 weeks follow-up since the last treatment prior to exiting the study. The minimum duration is therefore 96 weeks, and the maximum duration is approximately 108 weeks (for patients who received their last treatment at week 96 with 12 weeks posttreatment follow-up). Thus, patients could receive a maximum of 8 BOTOX treatment cycles. For details on how to analyze duration of exposure to study treatment see Section [6.1.1](#).

#### **3.4 Protocol Deviations**

Significant and non-significant deviations are defined in the Protocol Deviations Specification Document and will be determined prior to database lock. A protocol deviation table and patient listing will be produced for the significant protocol deviations. The deviation type and detail will be presented.

## **4. Demographics and Other Baseline Characteristics**

The procedures scheduled for baseline are to occur prior to receiving any study treatment.

Demographic and baseline characteristics will be summarized on the BOTOX-treated population according to the dose (grouped to the nearest dose group, ie, 25, 50, or 100 U of BOTOX) received at the first treatment cycle, as well as for the total of all BOTOX groups (ie, regardless of dose).

### **4.1 Demographics**

Age, race, sex, weight (kg), and height (cm) will be summarized by treatment group and overall. Race will be summarized as Caucasian, Black, Asian, Hispanic, and other, as well as just Caucasian or non-Caucasian (Black, Asian, Hispanic, and other).

### **4.2 Disease Characteristics**

Baseline characteristics, including the baseline daily average frequencies of urinary incontinence, urinary urgency, and urinary urgency incontinence, will be summarized according to treatment groups, as well as for the total of all BOTOX groups. Similarly, volume voided per micturition will be summarized according to treatment groups, as well as for the total of all BOTOX groups.

The following other baseline parameters will also be summarized by treatment group and overall: duration of OAB history and post-void residual (PVR) urine volume.

### **4.3 Prior Medications**

A prior medication is one taken prior to the first study treatment injection in the study. Summary tables for prior anticholinergic medications for OAB and prior non-anticholinergic medications for OAB will be provided according to WHO DDE preferred drug name and treatment groups, as well as for the total of all BOTOX groups.

### **4.4 Concomitant Medications/Procedures**

Concomitant medications are defined as those taken on or after the first study treatment, regardless of when the medications started. The number and percentage of patients taking each medication will be presented by WHO DDE preferred drug name for all BOTOX group.

All prophylactic antibiotic medication associated with study drug treatment will be summarized by WHO Drug Class and WHO DDE preferred drug name.

Concurrent procedures are defined as those undertaken on or after the first study treatment. A list of concurrent procedures will be provided for all BOTOX group.

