4.5 Permissible and Prohibited Medications/Treatments

4.5.1 Permissible Medications/Treatments

Therapy considered necessary for the patient's welfare may be given at the discretion of the investigator. Patients should be instructed to maintain a stable dose during the study whenever possible. All medications and adjunct therapies should be recorded on the appropriate electronic case report form (eCRF). If the permissibility of a specific medication/treatment is in question, please contact Allergan.

If the patient is already using psychiatric medications or medications for attention deficit hyperactivity disorder, they should have been on a stable dose prior to randomization/day 1 and agree to remain on the same dose during the study if possible when medically indicated.

Use of antihistamines and/or decongestants (sympathomimetics) is permitted to treat upper respiratory infections or allergies after study treatment has been administered.

Refer to Section 5.9.3 for information on permitted study treatment anesthesia.

If the permissibility of a specific medication/treatment is in question, please contact Allergan.

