4.5.2 Prohibited Medications/Treatments

The decision to administer a prohibited medication/treatment is done with the safety of the study participant as the primary consideration. When possible, Allergan should be notified before the prohibited medication/treatment is administered.

Botulinum toxin treatment of any serotype other than study drug is prohibited for any indication. Immunization to any botulinum toxin serotype is also prohibited during the study.

Anticholinergics or any other medications (including sympathomimetic medications) used for the treatment of symptoms of OAB, including nocturnal enuresis or nocturia, are prohibited throughout study participation. Desmopressin use is prohibited within 1 day of the start of the screening period procedures. Anticholinergic therapy is prohibited within 7 days of the start of the screening period procedures, or within 4 weeks if administered intravesically. Mirabegron is prohibited within 14 days of the start of the screening period procedures.

Administration of intravesical capsaicin or resiniferatoxin is prohibited during the study.

Use of electrical stimulation and neuromodulation devices (implanted and external) for the treatment of OAB are prohibited during study participation (if a patient is enrolled into the study with a device still implanted, it must be inactive at least 4 weeks prior to the first screening procedure; if a nonimplantable device is used, it must be discontinued at least 7 days prior to the first screening procedure).

Use of aminoglycoside antibiotic therapy is not permitted during study treatment administration. If a patient requires aminoglycoside antibiotic therapy during the trial, any study treatment administration must be delayed until the aminoglycoside antibiotic therapy is completed. Use of aminoglycoside antibiotics should also be avoided for 8 weeks after study treatment. Examples of such medications are: amikacin sulfate, gentamicin sulfate, kanamycin, tobramycin, netilmicin sulfate, and streptomycin.

Anticoagulant medications (eg, warfarin and other Coumadin derivatives), antiplatelet medications (eg, clopidogrel and aspirin [including low dose]) and any other medications with anticoagulative effects (eg, nonsteroidal anti-inflammatory drugs) are prohibited for a minimum of 3 days (or longer according to the clinical judgment of the investigator) prior to any study treatment, and must not be recommenced until the day following treatment.

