7.3.4 Safety Analyses

All safety analyses will be conducted on the BOTOX-treated population. Safety variables are adverse events, serious adverse events, physical examination, vital signs, laboratory tests (urinalysis, hematology, and clinical chemistry), renal function (eGFR), PVR urine volume, use of CIC, kidney and bladder ultrasound, immunogenicity testing, concomitant medications, concurrent procedures, and a urine pregnancy test for females who are postmenarche.

Medical Dictionary for Regulatory Activities (MedDRA) nomenclature will be used to code adverse events. For each adverse event reported, the number and percent of patients will be tabulated based on the preferred term. The tables will be generated by relationship to treatment as well as by primary system organ class and severity.

Data will be presented by BOTOX treatment cycle and grouped according to the actual dose received at that treatment cycle (grouped to the nearest dose group [25 U, 50 U, or 100 U BOTOX]), as well as by an overall BOTOX group (ie, regardless of dose).

As described in Section 6.3.15, immunogenicity samples will be analyzed using a 2-step process (toxin-binding and toxin-neutralizing antibodies). Results from both steps will be presented.

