## 1.3 Sample Size

The sample size calculation for this study is determined empirically. A total of approximately 108 patients are to be enrolled for the study (32 per treatment group plus 10% attrition).

The following table displays the estimated differences between 100 U of BOTOX (maximum 6 U/kg) and 25 U of BOTOX (maximum 6 U/kg) in mean daily average frequency of daytime episodes of urinary incontinence change from baseline at week 12 for a range of common standard deviations (SDs). All calculations assume 32 patients per treatment group and a 2-sided test significance level of 0.05. The calculation was performed using the commercial software nQuery Advisor (procedure MTC0-1), version 6.01 (Statistical Solutions Ltd., Cork, Ireland), and the CI for the difference of 2 means based on normal distribution.

Standard Deviation	Distance From Mean to the Limit
2.0	0.980
2.5	1.225
3.0	1.470
3.5	1.715
4.0	1.960

Note: The ranges of the SDs are determined based on the values from Allergan's 2 pivotal phase 3 OAB studies, 191622-095 and 191622-520. The estimate of the SD for the 100-U BOTOX treatment group is 3.33 for Study 191622-095, 3.58 for Study 191622-520, and 3.46 for the 2 studies combined. The distance from mean to limit indicates how much the CI for the mean extends from the observed difference in means in either direction.

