**15. Amendments**

Following is a summary of content-oriented changes that were made to each section of the SAP, and a brief rationale for these changes. Minor editorial and document formatting revisions have not been summarized.

Sections	Revision	Rationale
Section 1. Introduction	Revised to indicate that there will be no primary analysis, that only one analysis will be performed in this study	FDA agreed with Sponsor's request to stop further recruitment in this study, hence there was no longer a need for a primary analysis
Section 2.1: Analysis Populations	Deleted Per-protocol population. All analyses on per-protocol population were also deleted in other sections (e.g., Section 5.2.2)	To reflect current company practices on use of per-protocol population analyses
Section 2.1: Analysis Populations	Additional text included to clarify how participants are assigned to actual BOTOX treatment group based on actual BOTOX dose unit received	For added clarity
Section 2.1.1: Handling Mis-stratification	This section was added to discuss how mis-stratified patients will be handled in analysis	For added clarity
Section 2.2: Visit Windows	This section was modified by removing telephone visits	To reflect removal of telephone visits since minimal data is collected, and no data for which primary/secondary endpoints analyzed
Section 2.3: Data Conventions	Modified imputation rules for completely missing or partial dates for adverse events and prior/concomitant medications	To reflect current programming standard conventions
Sections 4.1 and 4.2: Demographics and Disease Characteristics	Deleted Summary of Pretreatment Adverse Events	To reflect current company standards
Section 5.2.1: Primary Analyses of Primary Efficacy Variables	Removed last paragraph describing how treatment by investigator interaction will be assessed	Due to the large number of sites and small number of patients per site, considered not feasible to assess treatment by investigator interaction
Section 5.4.6: Modified TBS	Added CMH test	To present between group-comparisons
Section 5.5: Dose response using AUC of primary efficacy measure	Section deleted	No longer considered an analysis of interest
Section 5.6: Subgroup Analyses for Primary Efficacy Variables	Replaced "investigator site" with "Region" as a subgroup	Due to the high number of sites and low sample size per site. Added "Region" as extrinsic factor.

Sections	Revision	Rationale

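### Concomitant medication is tabulated only for all doses pooled, against protocol 7.3.4, and no sensitivity analysis covers week 12 diaries recorded after a prohibited OAB treatment

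*SAP*

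**What the plan says.** **Tabulation.** SAP 4.4 counts as concomitant anything taken on or after the first study treatment and gives one presentation: "The number and percentage of patients taking each medication will be presented by WHO DDE preferred drug name for all BOTOX group". Concurrent procedures are listed the same way. Protocol 7.3.4 names concomitant medications and concurrent procedures as safety variables and states: "Data will be presented by BOTOX treatment cycle and grouped according to the actual dose received at that treatment cycle", with an overall column in addition. SAP 13 reports no departures from the protocol, and the change table in SAP 15 gives no reason for pooling.

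**Prohibited treatment.** Protocol 4.5.2 bars anticholinergic drugs and, in the same sentence, states that "any other medications (including sympathomimetic medications) used for the treatment of symptoms of OAB, including nocturnal enuresis or nocturia, are prohibited throughout study participation". Neuromodulation devices for OAB are also barred. The same section foresees that a prohibited treatment may still be given for the participant's safety. The specific withdrawal criteria in protocol 8.8 do not name such use.

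**Efficacy analysis.** SAP 2.1 defines one population, all treated patients. Under SAP 2.3.1 a diary day is valid if any urinary episode is recorded. The primary ANCOVA (SAP 5.2.1) contains baseline and treatment group. The one sensitivity analysis (SAP 5.2.2) is an MMRM on all observed data up to week 12, aimed at the LOCF rule. The per-protocol analysis is gone; SAP 15 records: "All analyses on per-protocol population were also deleted in other sections".

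**The concern.** The protocol itself treats OAB drugs as able to move the endpoint. It requires washout before the first screening procedure (7 days for oral anticholinergics, 14 for mirabegron), so baseline diaries are recorded off drug. A week 12 diary recorded on such a drug is not comparable with that baseline.

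The comparator is an active low dose, and retreatment is barred for 12 weeks. If patients with a poor response turned to an OAB drug in the meantime, and did so more often at 25 U, the 25 U mean change would improve for a reason unrelated to study dose. The 100 U versus 25 U difference would move towards zero. That test also gates 50 U versus 25 U in the fixed sequence.

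A reader of the study report would want to see, by dose, who started an OAB treatment before the week 12 diary, and whether the contrast holds without those diaries. The plan commits to neither.

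**Working it through.** **1. Is the pooling deliberate wording?** Three places in the SAP can be compared.
- SAP 4.3 presents prior OAB drugs by treatment group and in total.
- SAP 5.1 lists dose group and the all-BOTOX group as separate items.
- SAP 4.4 names only the all-BOTOX group, with no cycle and no window.

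Read together, SAP 4.4 specifies a single pooled column. Follow-up can run to 108 weeks, so drugs taken before week 12 of cycle 1 would be counted together with later use.

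**2. What a pooled column hides.** Assume use of 25%, 15% and 5% at 25, 50 and 100 U with equal arms. The pooled figure is (25 + 15 + 5)/3 = 15%, the same as 15% in every arm.

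**3. The plan's own precision figures (SAP 1.3).** Inputs: "All calculations assume 32 patients per treatment group and a 2-sided test significance level of 0.05". Half-width = 1.96 × SD × √(2/32) = 0.49 × SD.

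| SD | Computed | SAP |
|---|---|---|
| 2.0 | 0.980 | 0.980 |
| 2.5 | 1.225 | 1.225 |
| 3.0 | 1.470 | 1.470 |
| 3.5 | 1.715 | 1.715 |
| 4.0 | 1.960 | 1.960 |

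All five agree. The total also agrees: 32/0.9 = 35.6, rounded up to 36 per arm, × 3 = 108. At the adult SD of "3.46 for the 2 studies combined" the half-width is 0.49 × 3.46 = 1.695.

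**4. Size of the possible shift.** The documents give neither rates of use nor a drug effect, so every input here is an assumption.

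Shift towards zero = (share using at 25 U − share using at 100 U) × benefit in users.
- Low: (0.10 − 0.03) × 0.5 = 0.035 episodes/day, which is 0.035/1.695 = 2% of the half-width.
- High: (0.20 − 0.05) × 1.5 = 0.225 episodes/day, which is 0.225/1.695 = 13% of the half-width.

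**5. What that would do to the test.** The SAP states no power and no target difference. For illustration, take a true difference of 2.0, SD 3.46 and 32 per arm. The standard error is 3.46 × 0.25 = 0.865, and power = Φ(difference/0.865 − 1.96).

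| Shift | Remaining difference | Power |
|---|---|---|
| 0 | 2.000 | 63.8% |
| 0.035 | 1.965 | 62.2% |
| 0.225 | 1.775 | 53.7% |
| 0.40 | 1.600 | 45.6% |

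The last row is a more extreme assumption: a 20-point excess × 2 episodes/day. Two episodes/day is the top of the adult advantage of 100 U over placebo implied by protocol section 1 (2.5 to 3.0 against about 1, so 1.5 to 2.0). It is shown as an outer bound only.

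**The case against.** **Such use would not be wholly invisible.** A reader might infer that no output could reveal it. The documents do not support that. SAP 3.4 plans a table and patient listing of significant deviations with type and detail, and SAP 2.3 implies dated medication listings. What stands is narrower: the definition of significant sits in a separate document, SAP 3.4 states no dose split, and a listing has to be assembled by hand. SAP 6 also carries a general by-dose rule for safety analyses, but concomitant medication is placed in SAP 4 under its own sentence, which pools.

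**The deleted per-protocol set.** It is tempting to say that it would have removed these patients. Protocol 7.1 excludes only major deviations and leaves the criteria to the SAP. Nothing shown says that prohibited OAB treatment was one, so that argument is not made here.

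**Cold and allergy remedies.** A reader might see a contradiction between the ban above and this permission: "Use of antihistamines and/or decongestants (sympathomimetics) is permitted to treat upper respiratory infections or allergies after study treatment has been administered". There is none. The ban concerns use for OAB symptoms, and nothing suggests that colds or allergies differ between randomised arms.

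**The mechanism is uncertain.** Entry requires inadequate management on anticholinergics, so many patients have little reason to restart them. Patients who plan to use OAB treatment are excluded. Retreatment needs at least one daytime urgency incontinence episode in the diary, so suppressing symptoms could work against qualifying. These points are fair. They make both the rate of use and its direction uncertain, which is a reason to tabulate by dose.

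**Keeping all diaries is legitimate.** Estimating the effect regardless of other treatment is an accepted choice. But here it follows from silence, not from a stated rule, and nothing tests it.

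**Conclusion.** The point holds in two limited parts.

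First, SAP 4.4 contradicts protocol 7.3.4 on how concomitant medication is presented, and SAP 13 does not declare it. This rests on the text alone.

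Second, the plan neither states how week 12 diaries after a prohibited OAB treatment are handled nor checks their effect. Retention is an inference from the validity rule, the single population, the model and the MMRM data rule.

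The effect on the dose contrast is unknown. Higher use at 25 U is an assumption. On the inputs above the shift is 0.04 to 0.23 episodes/day, small beside a half-width of about 1.7. A reader might infer that a null result would be explained by background OAB drugs; the documents do not support that, and imprecision is the larger explanation. The half-width assumes 32 per arm. SAP 15 says recruitment was stopped and the achieved number is not given; with smaller arms the interval would be wider and each user would weigh more.

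This is a change that should be made, not one on which the trial's validity depends.

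**What to change.** 1. **SAP 4.4 and 13.** Present concomitant medications by treatment cycle and actual dose group, keeping the all-BOTOX column. Add a separate by-dose table of OAB-directed drugs or devices started between Day 1 and the week 12 diary of cycle 1. Correct SAP 13 so that it no longer says there are no deviations while any remain.
2. **SAP 5.2.2 and 5.3.1.** Keep the primary analysis unchanged and state that it uses all observed diaries regardless of such treatment. Add a supportive MMRM with diaries after the start of a prohibited OAB treatment set to missing. Add a week 12 responder analysis that counts those patients as non-responders.

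The MMRM has a downside: it answers a different question from the primary analysis and rests on a missing-at-random assumption that cannot be tested. It should be labelled supportive.

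The cost is SAP wording, extra table columns, one new table and two runs. Medication and adjunct therapy are already asked about at each visit and recorded in the eCRF (protocol 4.5.1 and 8.6), so trial conduct does not change.

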#### **4.5 Medical History and Surgical History**

Data for medical history with onset date prior to the first study treatment will be tabulated and presented for treatment groups as well as for the total of all BOTOX groups.

A list of surgical history will also be provided.

### **5. Efficacy Analyses**

All efficacy analyses will be performed on the BOTOX-treated population. The primary timepoint will be week 12 after treatment 1. Efficacy data will be presented by study visit in each BOTOX treatment cycle.

#### **5.1 Collection of Primary Efficacy Measurement(s) and Derivation of Primary Efficacy Variable(s)**

The following efficacy measures will be collected and summarized by BOTOX treatment cycle, BOTOX dose group, and all BOTOX group on the BOTOX-treated population:

- number of daytime urinary incontinence episodes
- number of daytime micturition episodes
- number of daytime urgency episodes
- presence or absence of nighttime urinary incontinence
- volume voided per micturition
- time to patient's request and time to patient's qualification for retreatment
- pediatric incontinence questionnaire (PinQ) score
- modified treatment benefit scale (TBS)

Change from study baseline analyses will be performed. Study baseline is defined as the data collected prior to the first treatment.

## 5.2 Primary Efficacy Analyses

For each of the BOTOX doses of 100 and 50 U, the null hypothesis to test is that there is no treatment difference between these dose groups and the 25 U BOTOX dose group in mean change from study baseline in daily average frequency of daytime urinary incontinence episodes at week 12 post-treatment 1. The alternative hypothesis is that there is a treatment difference in mean change from study baseline in daily average frequency of daytime urinary incontinence episodes at week 12 post-treatment 1.

